12.4 Response Evaluation Criteria in Solid Tumors

RECIST 1.1* will be used in this study for assessment of tumor response. While either CT or MRI may be utilized, as per RECIST 1.1, CT is the preferred imaging technique in this study.

* As published in the European Journal of Cancer

12.5 ECOG Performance Status

Grade	Description
0	Fully active, able to carry on all pre-disease performance without restriction.
1	Restricted in physically strenuous activity but ambulatory and able to carry out work of light or sedentary nature, e.g., light housework, office work.
2	Ambulatory and capable of all self-care but unable to carry out any work activities. Up and about more than 50% of waking hours
3	Capable of only limited self-care, confined to bed or chair more than 50% of waking hours
4	Completely disabled. Cannot carry on any self-care. Totally confined to bed or chair
5	Dead.

* As published in Am. J. Clin. Oncol.: *Oken, M.M., Creech, R.H., Tormey, D.C., Horton, J., Davis, T.E., McFadden, E.T., Carbone, P.P.: Toxicity And Response Criteria Of The Eastern Cooperative Oncology Group. Am J Clin Oncol 5:649-655, 1982.* The Eastern Cooperative Oncology Group, Robert Comis M.D., Group Chair.

12.6 Common Terminology Criteria for Adverse Events

The descriptions and grading scales found in the revised NCI Common Terminology Criteria for Adverse Events (CTCAE) version 4.0 will be utilized for adverse event reporting. (https://ctep.cancer.gov/protocolDevelopment/electronic_applications/ctc.htm).

12.7 List of Abbreviations

Abbreviation/Term	Definition
1L	First Line
2L	Second Line
AE	Adverse Event
ADA	Anti-Drug Antibodies
ALT	Alanine Aminotransferase
ANC	Absolute Neutrophil Count
AP	Alkaline Phosphatase
APaT	All Patients as Treated
aPTT	Activated Partial Thromboplastin Time
ASCO	American Society of Clinical Oncology
AST	Aspartate Aminotransferase
AUC	Area Under the Curve
bid	Twice a Day
β-HCG	Beta Human Chorionic Gonadotropin
BSA	Body Surface Area
CBC	Complete Blood Count
CI	Confidence Interval
CIMP	CPG Island Methylator Phenotype
CIN	Chromosomal Instability
COPD	Chronic Obstructive Pulmonary Disease
CNS	Central Nervous System
CR	Complete Response
CRC	Colorectal Carcinoma
CrCl	Calculated Creatinine Clearance
CRF	Case Report Form
CSR	Clinical Study Report
CT	Computed Tomography
CTCAE	Common Toxicity Criteria for Adverse Events
CTLA-4	Cytotoxic T-Lymphocyte-Associated Antigen-4
dMMR	Deficient Mismatch Repair
DNA	Deoxyribonucleic acid
DOR	Duration of Response
DR	Drug Related
ECI	Events of Clinical Interest
ECG	Electrocardiogram
ECOG	Eastern Cooperative Oncology Group
EDC	Electronic Data Capture
EGJ	Esophagogastric Junction
eDMC	external Data Monitoring Committee
EOC	Executive Oversight Committee
EORTC	European Organisation for Research and Treatment of Cancer
ePRO	Electronic Patient Reported Outcomes
ERC	Ethics Review Committee
ESMO	European Society for Medical Oncology
FBR	Future Biomedical Research
FDA	Food and Drug Administration
FDAAA	Food and Drug Administration Amendments Act
FDAMA	Food and Drug Administration Modernization Act
FNA	Fine Needle Aspirate

Abbreviation/Term	Definition
GCP	Good Clinical Practice
GEP	Gene Expression Profile
GI	Gastrointestinal
GFR	Glomerular Filtration Rate
GFR	Glomerular Filtration Rate
HBsAg	Hepatitis B surface Antigen
HCV	Hepatitis C Virus
HEA	Health Economic Assessment
HIV	Human Immunodeficiency Virus
HNSCC	Head and Neck Squamous Cell Carcinoma
HPV	Human Papillomavirus
HR	Hazard Ratio
IB	Investigator's Brochure
ICF	Informed Consent Form
ICH	International Conference on Harmonization
IHC	Immunohistochemistry
INR	International Normalized Ratio
irAE	immune-related adverse event
irRECIST	Immune related RECIST (Modification of RECIST 1.1)
irRC	Immune related Response Criteria
IRB	Institutional Review Board
ITIM	Immunoreceptor Tyrosine-based Inhibition Motif
ITSM	Immunoreceptor Tyrosine-based Switch Motif
ITT	Intention To Treat
IV	Intravenous
IVRS	Interactive Voice Response System
IWRS	Integrated Web Response System
Kg	Kilogram
LDH	Lactate Dehydrogenase
mAb	Monoclonal Antibody
mCRC	Metastatic Colorectal Carcinoma
mcL	Microliters
MEL	Melanoma
Mg	Milligram
Mg/kg	Milligram per Kilogram
mL	milliliter
MRI	Magnetic Resonance Imaging
MSD	Merck Sharp & Dohme Corp., a subsidiary of Merck & Co., Inc.
MSI-H	Microsatellite Instability High
MTD	Maximum Tolerated Dose
NA or N/A	Not Applicable
NCCN	National Comprehensive Cancer Network
NCI	National Cancer Institute
NSAID	Non-Steroidal Anti-inflammatory Drug
NSCLC	Non-Small Cell Lung Cancer
ORR	Objective Response Rate
OS	Overall Survival
OTC	Over-the-counter
PBPK	Physiologically based pharmacokinetic
PD	Progressive Disease

Abbreviation/Term	Definition
PFS	Progression Free Survival
PGt	Pharmacogenetic
PIN	Personal Identification Number
PK	Pharmacokinetic
PK/PD	Pharmacokinetic/Pharmacodynamic
PO	Oral Administration
PR	Partial Response
PRO	Patient Reported Outcomes
PT	Prothrombin Time
PS	Performance Status
QoL	Quality of Life
R/M	Recurrent or Metastatic
RECIST	Response Evaluation Criteria in Solid Tumors
RNA	Ribonucleic Acid
RR	Response Rate
QoL	Quality of Life
Q2W	Every 2 Weeks
Q3W	Every 3 Weeks
Q9W	Every 9 Weeks
RT	Radiation Therapy
SAE	Serious Adverse Events
SAP	Statistical Analysis Plan
SCC	Squamous Cell Carcinoma
SD	Stable Disease
SFU	Survival Follow-Up
SGOT	Serum Glutamic Oxaloacetic Transaminase
SGPT	Serum Glutamic Pyruvic Transaminase
SIM	Site Imaging Manual
SOP	Standard Operating Procedures
TIL	Tumor Infiltrating Lymphocytes
TSH	Thyroid Stimulating Hormone
ULN	Upper Limit of Normal
WBC	White Blood Cell

12.8 Germany-specific Requirements

Section 5.1.3 Exclusion Criteria

Exclusion Criterion: HIV 1/2 antibodies testing is required for participants when the investigator has reason to suspect the patient has Human Immunodeficiency Virus infection or is otherwise mandated per local guidance.

Exclusion Criterion: Hepatitis B surface Antigen reactive and HCV RNA [qualitative] testing is only required when the investigator has reason to suspect the patient has an Hepatitis B, Hepatitis C infection or testing is mandated per local guidance.

1 INTRODUCTION

This supplemental SAP (sSAP) is a companion document to the protocol. In addition to the information presented in the protocol SAP which provides the principal features of confirmatory analyses for this trial, this supplemental SAP provides additional statistical analysis details/data derivations and documents modifications or additions to the analysis plan that are not “principal” in nature and result from information that was not available at the time of protocol finalization.

2 SUMMARY OF CHANGES

Section Number (s)	Section Title(s)	Description of Change (s)	Rationale
3.4.1.1	Primary Efficacy Endpoint	DOR definition updated	Using the most up to date DOR definition in oncology SAP template.
3.6.1	Statistical Methods for Efficacy Analyses	The Table 1: censoring rules for DOR; and Table 2: Censoring rules for PFS analysis are updated.	Updates are based on the changes of censoring rules in the latest SAP template.
3.6.1	Statistical Methods for Efficacy Analyses	Added the sentence: “The secondary and exploratory endpoints may be analyzed by populations as appropriate.”	The secondary and exploratory endpoints may also be analyzed by all three populations.
3.6.3	Summaries of Baseline Characteristics, Demographics, and Other Analyses	Paragraphs related to biomarker analysis are deleted.	The cutoffs of GEP “low”, “intermediate” and “high” have been pre-specified at -1.540 and -0.945.
3.6.4	Sample size	The sample size descriptions based on the different assumptions of “GEP intermediate or high”	The cutoffs of GEP “low”, “intermediate” and “high” have been pre-specified at -1.540

Section Number (s)	Section Title(s)	Description of Change (s)	Rationale
		and “GEP high”, respectively, are added.	and -0.945.

3 ANALYTICAL AND METHODOLOGICAL DETAILS

3.1 Statistical Analysis Plan Summary

Key elements of the statistical analysis plan are summarized below; the comprehensive plan is provided in Sections 3.2 to Section 3.9. There will be a separate PK analysis plan. Post hoc exploratory analyses will be clearly identified in the CSR.

Study Design Overview	A Phase II Study of Pembrolizumab Monotherapy in Third Line, Previously Treated Subjects with Advanced/Metastatic Adenocarcinoma or Squamous Cell Carcinoma of the Esophagus or Advanced/Metastatic Siewert Type I Adenocarcinoma of the Esophagogastric Junction (KEYNOTE – 180)
Treatment Assignment	This is a single arm open-label study.
Analysis Populations	All Subjects as Treated (ASaT)
Primary Endpoint(s)	ORR based on RECIST 1.1 assessed by central imaging vendor
Statistical Methods for Key Efficacy Analyses	95% CI for ORR will be calculated using the exact binomial distribution.
Statistical Methods for Key Safety Analyses	Count and percentage of AE will be provided.
Multiplicity	Not applicable since this is an estimation study.
Sample Size	The planned sample size is approximately 100 subjects. The primary objective of the study is to estimate ORR in all subjects, in subjects whose tumors classified as “GEP intermediate or high” ($GEP \geq -1.540$) and subjects whose tumors classified as “GEP high” ($GEP \geq -0.945$).

3.2 Responsibility for Analyses/In-House Blinding

The statistical analysis of the data obtained from this study will be the responsibility of the Clinical Biostatistics department of the SPONSOR.

This trial is being conducted as an open-label study, i.e., subjects, investigators, and SPONSOR personnel will be aware of subject treatment.

The Clinical Biostatistics department will generate the allocation schedule.

3.3 Estimation

Objectives of the study and estimation to be performed are stated in Section 3.0 in the protocol.

3.4 Analysis Endpoints

3.4.1 Efficacy Endpoints

3.4.1.1 Primary Efficacy Endpoint

- Objective response rate (ORR) - RECIST 1.1 assessed by central imaging vendor**

Objective response rate is defined as the proportion of the subjects in the analysis population who have a complete response (CR) or partial response (PR). Responses are based upon blinded central imaging vendor assessments per RECIST 1.1.

3.4.1.2 Secondary Efficacy Endpoints

- Disease Control Rate (DCR) - RECIST 1.1 assessed by central imaging vendor**

Disease control rate (DCR) is defined as the percentage of subjects who have achieved confirmed CR or PR or have demonstrated SD prior to any evidence of progression.

- Duration of Response (DOR) - RECIST 1.1 assessed by central imaging vendor**

For subjects who demonstrate CR or PR, duration of response is defined as the time from first documented evidence of CR or PR until disease progression or death due to any cause, whichever occurs first.

- Progression-free Survival (PFS) - RECIST 1.1 assessed by central imaging vendor**

PFS is defined as the time from first day of study treatment to the first documented disease progression or death due to any cause, whichever occurs first.

- **Overall survival (OS)**

OS is defined as the time from first day of study treatment to death due to any cause. Subjects without documented death at the time of the final analysis will be censored at the date of the last follow-up.

3.4.1.3 Exploratory Efficacy Endpoints

- **Progression-free Survival (PFS) - irRECIST assessed by central imaging vendor**

Progression-free-survival (PFS) is defined as the time from first day of study treatment to the first confirmed disease progression or death due to any cause, whichever occurs first.

- **ORR -- irRECIST assessed by central imaging vendor**

Overall response rate is defined as the proportion of the subjects in the analysis population who have a complete response (CR) or partial response (PR). Responses are based upon blinded central imaging vendor assessments per irRECIST.

- **Duration of Response (DOR) - irRECIST assessed by central imaging vendor**

For subjects who demonstrated CR or PR, response duration is defined as the time from the date of first response (CR or PR) until the date of confirmed disease progression or death.

3.4.2 Safety Endpoints

Safety measurements are described in Section 7 Trial Procedures in the protocol.

3.5 Analysis Populations

3.5.1 Efficacy Analysis Populations

The All Subjects as Treated (ASaT) population will be used for the analysis of ORR, DCR, PFS, and OS. The ASaT population consists of all allocated subjects who received at least one dose of study treatment.

The analysis population for DOR consists of responders.

Details on the approach to handling missing data are provided in Section 3.6 Statistical Methods.

3.5.2 Safety Analysis Populations

The All Subjects as Treated (ASaT) population will be used for the analysis of safety data in this study. The ASaT population consists of all allocated subjects who received at least one dose of study treatment.

At least one laboratory or vital sign measurement obtained subsequent to at least one dose of study treatment is required for inclusion in the analysis of each specific parameter. To assess change from baseline, a baseline measurement is also required.

Details on the approach to handling missing data for safety analyses are provided in Section 3.6 Statistical Methods.

3.6 Statistical Methods

3.6.1 Statistical Methods for Efficacy Analyses

This section describes the statistical methods that address the primary and secondary objectives.

For the primary efficacy endpoint of ORR, the point estimate and 95% confidence interval will be provided using exact binomial method proposed by Clopper and Pearson (1934)[Ref. 5.4: 03RMKM]. Subjects in the primary analysis population (ASaT) without ORR data will be counted as non-responders.

For DCR, the point estimate, 95% confidence interval will be provided using the exact binomial method proposed by Clopper and Pearson (1934)[Ref. 5.4: 03RMKM]. Subjects in the analysis population (ASaT) with missing DCR data are considered as disease not under control.

For DOR, Kaplan-Meier (KM) curves and median estimates from the KM curves will be provided, as appropriate. Subjects who are alive, have not progressed, have not initiated new anti-cancer treatment, and have not been determined to be lost to follow-up are considered ongoing responders at the time of analysis. Censoring rules for DOR are summarized in [Table 1](#).

Table 1. Censoring Rules for DOR

Situation	Date of Progression or Censoring	Outcome
No progression nor death, no new anti-cancer therapy initiated	Last adequate disease assessment	Censored (non-event)
No progression nor death, new anti-cancer therapy initiated	Last adequate disease assessment before new anti-cancer therapy initiated	Censored (non-event)
≥ 2 consecutive missed disease assessments at any time prior to progression or death	Last adequate disease assessment prior to ≥ 2 missed adequate disease assessments	Censored (non-event)
Death or progression after ≤ 1 missed adequate disease assessments	PD or death	End of response (Event)

A missed disease assessment includes any assessment that is not obtained or is considered inadequate for evaluation of response. Subjects are considered to have an ongoing response if censored, alive, have not progressed, have not started a new anti-cancer therapy, have not had ≥ 2 consecutive missed disease assessments, and have not been determined to be lost to follow-up.

For PFS and OS endpoints, Kaplan-Meier (KM) curves and median estimates from the KM curves will be provided, as appropriate. The censoring rules for PFS are summarized in [Table 2](#). The efficacy analysis is summarized in [Table 3](#). The secondary and exploratory endpoints may be analyzed by populations as appropriate.

Table 2 Censoring rules for PFS analysis

Situation	Primary Analysis
No PD and no death; new anticancer treatment is not initiated	Censored at last disease assessment
No PD and no death; new anticancer treatment is initiated	Censored at last disease assessment before new anticancer treatment

Table 3 Analysis Strategy for Efficacy Variables

Endpoint/Variable [‡] (Description, Time Point)	Statistical Method	Analysis Population	Missing Data Approach
Primary Endpoint and Hypothesis			
ORR • RECIST 1.1, Central imaging vendor assessment	Exact method based on binomial distribution	ASaT • All subjects • Subjects whose tumors classified as “GEP intermediate or high” (GEP \geq -1.540) • Subjects whose tumors classified as “GEP high” (GEP \geq -0.945)	Subjects with missing data are considered non-responders

Endpoint/Variable [‡] (Description, Time Point)	Statistical Method	Analysis Population	Missing Approach	Data
Secondary Endpoints				
DCR • RECIST 1.1, Central imaging vendor assessment	Exact method based on binomial distribution	ASaT	Subjects with missing data are considered as disease not under control	
DOR • RECIST 1.1, Central imaging vendor assessment	Summary statistics using Kaplan-Meier method	All responders	Non-responders are excluded from analysis	
PFS • RECIST 1.1, Central imaging vendor assessment	Summary statistics using Kaplan-Meier method	ASaT	Censoring rules follow Table 2 .	
OS	Summary statistics using Kaplan-Meier method	ASaT	Censored at last known alive date	
Exploratory Endpoints				
ORR • irRECIST, Central imaging vendor assessment	Exact method based on binomial distribution	ASaT • All subjects • Subjects whose tumors classified as “GEP intermediate or high” (GEP \geq - 1.540) • Subjects whose tumors classified as “GEP high” (GEP \geq - 0.945)	Subjects with missing data are considered non-responders	

Endpoint/Variable [‡] (Description, Time Point)	Statistical Method	Analysis Population	Missing Data Approach
PFS • irRECIST, Central imaging vendor	Summary statistics using Kaplan-Meier method	ASaT	Censoring rules per irRECIST also follow Table 2 . If there is no confirmation scan available after the initial PD scan, then it is considered as a PFS event at the initial PD scan time point.
DOR • irRECIST, Central imaging vendor	Summary statistics using Kaplan-Meier method	All responders	Non-responders are excluded from analysis; If there is no confirmation scan available after the initial PD scan, then it is considered as a PFS event at the initial PD scan time point.

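### sSAP Table 1 censors DOR after any earlier two-scan gap, even when adequate scans resumed in response, and rows 1, 3 and 4 do not fit together; the expected effect is small

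*Combined protocol and SAP*

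**What the plan says.** sSAP 3.4.1.2 sets the endpoint: "duration of response is defined as the time from first documented evidence of CR or PR until disease progression or death due to any cause". Table 1 in sSAP 3.6.1 then gives the censoring rules:

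- **Row 1**, "No progression nor death, no new anti-cancer therapy initiated": censored at the last adequate assessment. Earlier gaps are not mentioned.
- **Row 3**, two or more "consecutive missed disease assessments at any time prior to progression or death": censored at the "Last adequate disease assessment prior to ≥ 2 missed adequate disease assessments".
- **Row 4**, "Death or progression after ≤ 1 missed adequate disease assessments": an event on that date.

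The note below the table adds: "A missed disease assessment includes any assessment that is not obtained or is considered inadequate for evaluation of response". It counts a response as ongoing only for subjects who, among other conditions, "have not had ≥ 2 consecutive missed disease assessments, and have not been determined to be lost to follow-up". The paragraph above the table also describes ongoing responders, but without any condition on missed scans.

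Table 2 (PFS) has no missed-scan rule. Imaging is every 9 weeks (protocol 7.1.4.1.2). The sSAP's summary of changes attributes the current DOR rules to a template update and gives no trial-specific reason.

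**The concern.** A missed-scan rule is meant for progression found straight after a long gap, when its date is uncertain. Row 3 reaches further. Once adequate scans have resumed and still show response, the old gap says nothing about when a later progression occurred, yet that progression is removed.

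Because row 1 has no gap condition, the subject's follow-up is cut back only once progression or death is seen. Removing time only from subjects who go on to have an event is informative censoring. DOR is a named secondary objective and may rest on few responders (17 in the lowest row of sSAP Table 4), so one reclassified long responder would be visible. Gaps are plausible, since the protocol asks only for best efforts to keep imaging after treatment stops (7.1.4.1.3).

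**Working it through.** **1. One subject on the 9-week schedule.** First response week 9; adequate scan week 18; weeks 27 and 36 missed; still in response at weeks 45, 54 and 63; progression at week 72.

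| Rule applied | Result |
|---|---|
| Row 1, data cut just before week 72 | censored, 63 − 9 = 54 weeks |
| Row 3, once progression is seen | censored, 18 − 9 = 9 weeks |
| Row 4, counting misses directly before progression (none) | event, 72 − 9 = 63 weeks |
| PFS Table 2 | the same progression is an event |

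The week-63 scan places the progression within one 9-week interval. Observing it nevertheless reduces the subject's contribution from 54 to 9 weeks.

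**2. What row 4 counts.** If it counts misses directly before the event, this subject meets rows 3 and 4 together, and no precedence is given. If it counts all misses since response, consider a subject who misses weeks 27 and 45 singly and then progresses. Row 3 fails (not consecutive), row 4 fails (two misses), and rows 1 and 2 fail (progressed). No row applies.

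**3. Ongoing response.** Take the subject in step 1 at a cut-off just after week 63. The paragraph above Table 1 makes this an ongoing response; the note below it does not.

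**4. Events lost.** The plan states no figure that depends on Table 1, so there is none to reproduce, and it gives no miss rate. The size comes from simulation (20,000-40,000 responders per scenario). Assumptions: exponential DOR with median 40 weeks (the figure for the earlier esophageal cohort in protocol 4.2.1) or 80 weeks; scans every 9 weeks; follow-up of 52-104 weeks after response. The table gives the share of observed events lost only because of an earlier gap that had closed.

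| Assumed misses | Share lost |
|---|---|
| 5%, independent | 0.3-0.4% |
| 10%, independent | 1.3-1.6% |
| 10-20%, clustered (40-50% chance the next is missed too) | about 3-7% |

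Depending on how clustering is set up, the last row can run from 2.5% to 9.5%. With a 20-week median the first two rows fall to about 0.2% and 0.7%.

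At median 40 weeks and 10% independent misses, 70.6% of responders have an observed progression and 1.27% of those are lost:
- 17 responders: 17 × 0.706 × 0.0127 = 0.15 progressions.
- 35 responders: 35 × 0.706 × 0.0127 = 0.31 progressions.

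Seventeen responders give about 17 × 0.706 = 12 events. The chance of losing at least one is 1 − (1 − q)^12: 4% at q = 0.3%, 18% at 1.6%, 31% at 3% and 58% at 7%.

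**5. Effect on the Kaplan-Meier curve at 78 weeks.**

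| Scenario (overall miss rate, clustering) | Row 3 literal | Gap immediately before event only | No missed-scan censoring |
|---|---|---|---|
| Median 40, 10%, 40% | 0.312 | 0.307 | 0.291 |
| Median 80, 20%, 50% | 0.599 | 0.581 | 0.542 |

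The literal rule lies 0.5 and 1.8 points above the narrowed rule. The narrowed rule still keeps most of the shift away from counting every event: (0.307 − 0.291)/(0.312 − 0.291) = 76%, and (0.581 − 0.542)/(0.599 − 0.542) = 68%.

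The difference between the literal and narrowed rules shows only late. At 52 weeks (median 40, independent misses) they give 0.466 against 0.467 at 10% missed and 0.488 against 0.494 at 20%.

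The median is 45 weeks under both rules at 5%, 10% and 20% independent misses when the true median is 40. With a true median of 80 and 20% missed it moves by one scan interval (99 against 90).

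**The case against.** **Row 4 can be read as the complement of row 3**, covering every event without two consecutive misses. Each subject then gets one answer. This stands: a reader might infer that Table 1 flatly contradicts itself, but that needs the word *immediately* read into row 4, which is not there. The complement reading in turn needs *consecutive* read in. The text is ambiguous rather than contradictory. On any of these readings row 3 still discards the well-dated progression.

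**The note on ongoing response hints that a two-scan gap ends evaluable follow-up for everyone.** If row 3 also applied to responders without an event, the 78-week rates in the two scenarios would be 0.289 and 0.538, against 0.291 and 0.542 with no missed-scan censoring, so the upward shift would vanish. The tilt therefore depends on taking row 1 as written. Row 1 has no gap condition and row 3 speaks of a gap before an event, so that is the natural reading. Applying row 3 to all would still discard usable follow-up.

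**The size is driven by assumptions and lies within sampling noise.** This also stands. Miss rates, clustering and the 12 events are not in the documents. With 17 responders the binomial standard error near 0.3 is √(0.3 × 0.7/17) = 0.11, or 11 points, and the plan names KM curves and medians, not a 78-week rate. The defect is systematic and cheap to remove, but it will not change the trial's message.

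**Conclusion.** The concern holds as a defect in a stated rule. Row 3 as written drops progressions whose dates are well determined, and with row 1 it makes censoring depend on the outcome. Row 4 either overlaps row 3 or leaves a case uncovered unless a word is supplied. The two ongoing-response descriptions differ on missed scans.

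The expected effect is small: about 0.3-1.6% of observed events at 5-10% independent misses, about 3-7% with clustering, up to about 2 points on the 78-week rate, and usually no change in the median. All of this rests on the assumed miss patterns and the exponential model. A reader might infer that the reported DOR will be materially inflated; the documents do not support that, since they give no miss rate. Nor would narrowing row 3 remove the upward shift, because roughly 70-75% of it remains in the scenarios above.

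ORR, PFS and OS are unaffected. For a secondary, descriptive endpoint in a single-arm estimation study, this is a minor point that is still worth correcting.

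**What to change.** In sSAP 3.6.1, before database lock:

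1. Table 1 row 3: *Progression or death immediately after 2 or more consecutive missed disease assessments (no adequate assessment between the gap and the event)*.
2. Table 1 row 4: *Progression or death immediately after at most 1 missed assessment*.
3. Keep one definition of ongoing response, counting only misses immediately before the data cut-off.
4. Add a sensitivity DOR analysis that treats every observed progression or death as an event, in line with PFS Table 2. It is needed because the narrowed rule still censors some events.

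The cost is a few words, one programming condition and one extra output. No new data are needed, and settling the wording before lock avoids choosing a reading once the events are known.

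### Do the sSAP censoring tables leave PFS or DOR undetermined when a subject progresses or dies after new anti-cancer therapy?

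*Combined protocol and SAP*

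**What the plan says.** The sSAP, section 3.4.1.2, states: "PFS is defined as the time from first day of study treatment to the first documented disease progression or death due to any cause". Table 2 in sSAP 3.6.1 then gives two situations in which PFS is censored, both limited to subjects with neither progression nor death. One is for subjects without new therapy. The other reads "No PD and no death; new anticancer treatment is initiated", with the outcome "Censored at last disease assessment before new anticancer treatment".

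Table 1, for DOR, has the same two situations and two more. It censors after "≥ 2 consecutive missed disease assessments at any time prior to progression or death" and counts an event for "Death or progression after ≤ 1 missed adequate disease assessments". The text below it explains: "A missed disease assessment includes any assessment that is not obtained or is considered inadequate for evaluation of response".

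In Table 3 of the sSAP, the exploratory irRECIST DOR row says of an unconfirmed progression: "then it is considered as a PFS event at the initial PD scan time point". The reason given for both censoring tables, in sSAP section 2, is "Updates are based on the changes of censoring rules in the latest SAP template". Neither protocol Section 8 nor the sSAP plans a sensitivity analysis of PFS or DOR.

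**The concern.** PFS and DOR rest on central review, while the site's reading drives treatment and the move to survival follow-up (protocol 7.1.4.1.6 and 7.1.6.3.3). Study imaging stops at new therapy or at documented progression (7.1.4.1.2 and 7.1.4.1.3), but deaths are still collected. A subject can therefore leave imaging without central progression and die months later. Under Table 2 that death is an event on its own date. The same subject, if alive at the cut-off, is censored back at the last scan. Whether follow-up time after the last scan counts then depends on the outcome, which could distort the curve.

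Table 1 seems to treat the same death differently. If the scans not done after imaging stopped count as missed, DOR is censored while PFS has an event. With no control arm, such an effect cannot cancel between groups, and no planned output would show its size.

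**Working it through.** **The plan's own figures.** The only computed design figures are the exact ORR intervals in sSAP Tables 4 to 6. The lower limit is the 2.5% quantile of Beta(x, n−x+1) and the upper limit is the 97.5% quantile of Beta(x+1, n−x). All 11 rows reproduce, for example 17/100 (10.2, 25.8), 21/60 (23.1, 48.4) and 14/40 (20.6, 51.7). None depends on the PFS or DOR rules.

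**Is any PFS outcome undetermined?** Set the definition beside Table 2:

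- Documented progression or death, with or without new therapy: an event, by sSAP 3.4.1.2.
- Neither, and no new therapy: Table 2, first row.
- Neither, and new therapy: Table 2, second row.

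These cases are exclusive and cover everyone. Table 2 lists censoring situations, so it needs no event row. Because imaging ends when new therapy starts, the last scan before new therapy is normally the last scan of all, and the two rows give the same date.

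**One subject, worked through** (an unusual case): response at week 9, last scan at week 18, new therapy at week 20, cut-off at week 52.

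- PFS: death at week 40 is an event at 40; alive at cut-off is censored at 18.
- DOR after death at week 40: an event at 40 − 9 = 31 weeks, or censored at 18 − 9 = 9 weeks if the week 27 and week 36 scans count as missed.

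The PFS result is fixed by the text. The DOR result depends on what *missed* means.

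**Size for PFS.** The documents give no rates for these paths, so all inputs are assumed: median time to site progression 9 or 12 weeks; median survival after it 12 or 16 weeks; 10, 20 or 30% of site progressions not called centrally; central progression following after a mean of 9 or 27 weeks, or never; three follow-up ranges. That makes 2 × 2 × 3 × 3 × 3 = 108 scenarios, run under five scan models (fixed 9-weekly scans or ±7 days, with differing shares of repeat scans).

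- 26-week PFS, Table 2 minus full central follow-up: −2.9 to +3.2 points. If 80% have a repeat scan: −2.1 to +1.7.
- Standard error for a 30% rate: √(0.3 × 0.7 / 100) = 0.046, or 4.6 points.
- Median PFS: −0.4 to +0.3 weeks.
- Compared with consistent censoring and with counting site progression as an event, Table 2 was closest to full follow-up in 81 to 107 of the 108 scenarios, depending on the model.

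That model has no separate rate of new therapy. A simpler one assumes that 10, 20 or 30% start new therapy before central progression, with a median of 5 months from then to death and a latent median PFS of 3 months. Six-month PFS was 0.41, 0.43 and 0.46 with later death as an event, against 0.40, 0.42 and 0.45 with censoring at the last scan before new therapy. The choice is worth about one point.

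**Size for DOR.** The median from response to site progression is set at 40 weeks, the median DOR in protocol 4.2.1. The other inputs are assumed (18 scenarios).

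- Share of responders with a PFS event but censored DOR: 0.4 to 4.3%. For the 17 to 35 responders in sSAP Table 4: 0.004 × 17 = 0.1 to 0.043 × 35 = 1.5 subjects.
- The two readings of *missed* differ by at most 0.6 points in the 43-week DOR rate.
- In the simpler model with 25 responders, the 12-month rates under the two readings are 0.460 and 0.464, 0.464 and 0.469, and 0.463 and 0.475, so 0.4 to 1.2 points apart. Ignoring censoring, the standard error is √(0.46 × 0.54 / 25) = 0.10, or 10 points.

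**The irRECIST DOR row.** The sSAP 3.6.1 text assigns DOR censoring to Table 1 without limiting it to RECIST 1.1, and the RECIST 1.1 DOR row in Table 3 cites no table either. What remains is the name of the wrong endpoint in the irRECIST row, where the meaning is plain.

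**The case for a change.** The best case for a change is the missing sensitivity analysis. In a single-arm, open-label study the curves are all the reader has, and site assessments and new-therapy starts are already collected (protocol 7.1.1.6.3, 7.1.4.1.6 and 7.1.6.3.2). Counting site progression as an event puts 26-week PFS 1.4 to 3.3 points below Table 2 if 10% of site progressions are not called centrally, and about 4 to 10 points below at 30%, which can exceed the standard error. In the simpler model, counting new therapy as an event costs about 5 to 16 points. Two programmers could also read *missed* differently and both be within the text.

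The last point stands as a gap in wording, but a small one. A scan is ordinarily missed only if it was due, and either reading gives nearly the same curve.

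The larger differences measure the distance to another estimand, not an error in this one. That estimand is itself unsettled: site progression could mean the first radiologic finding or the irRECIST-confirmed one, and the first would count the tumor flare that the protocol lets subjects be treated through. Nor would a pair of alternatives reliably bracket the planned result. Consistent censoring lay 0.6 to 5.3 points above Table 2 in the fixed-scan models but about one point below it in the simpler model. Such analyses may interest readers, but the plan's results do not depend on them, and protocol Section 8.0 already requires post hoc exploratory analyses to be identified in the CSR.

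**Conclusion.** No change is needed. The definition and Table 2 together determine every subject's PFS outcome, and handling missed scans differently for PFS and DOR is a legitimate choice even with only a template as its reason. The estimated distortion of PFS is below one standard error, with no consistent direction. The open meaning of *missed* is a gap that analysts can fill sensibly, and the wrong endpoint name in the irRECIST DOR row is clerical. PFS and DOR are secondary, descriptive endpoints in an estimation study without hypothesis tests.

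The sizes rest on assumed discordance, survival and follow-up. The DOR figures also lean on a 40.0-week median from only 7 responders, which equals the top of its reported range. The finding that no PFS outcome is left open rests on the text alone.
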